4.9.2.5 Other Safety Measures

4.9.2.5.1 Overdose

The incidence of TEAEs associated with overdose will be summarized by MedDRA SOC and PT, if applicable.

4.9.2.5.2 Physical Examination and Weight

A complete physical examination will include, at a minimum, assessments of the following organs/body systems: head, ears, eyes, nose, throat, lungs, heart, abdomen, skin, and extremities. The observed values and the changes from baseline in the weight and body mass index (BMI) will be summarized. Adverse changes from baseline in physical examination findings will be classified as AEs and analyzed accordingly.

4.9.2.5.3 Local injection tolerability

The incidence of TEAEs associated with local injection tolerability will be summarized by MedDRA HLT injection site, if applicable.

4.10 Pharmacokinetic (PK) Analyses

Individual PK data will be collected for all participants. PK analyses will be performed on the PK analysis set.

Serum concentrations will be summarized descriptively by treatment and by visit with descriptive statistics including the number of observations, arithmetic mean, SD,

median, minimum, maximum, coefficient of variation, geometric mean, and geometric coefficient of variation.

Mean (\pm SD) serum concentration versus scheduled time profiles will be presented graphically. Actual dose administration and sampling times will be used for all calculations.

[REDACTED]

4.13 Immunogenicity

The ADA status will be summarized by the categories defined in [Table 6](#). The ADA incidence rate may also be summarized by treatment group at each time point, where the incidence is the proportion of the participants with ADA positive results post-baseline only or boosted their pre-existing ADA during the study period. The cutoff for the

[figure not shown]
boosted ADA will be determined before the database lock for the primary analysis. The impact of ADA on PK will be assessed. If data allow, any confirmed ADA positive samples will be tested for ADA titer and the presence of neutralizing antibodies to daxdilimab. The number and percentage of participants who develop positive ADA will be summarized by randomized treatment group, and the impact of ADA on efficacy and safety will be evaluated.

[figure not shown]
The ADA summary will be produced for Stage I using Safety Analysis Set and for the overall study using Any Daxdilimab Analysis Set. For the overall study summary, the baseline positive is defined as any positive ADA prior to the first administration of daxdilimab.

Table 6 Definition of ADA Status

ADA Status	Definition
Prevalence (Positive during the study)	ADA positive observed at least once during the study (baseline included)
Negative during the study	ADA positive not observed at any visit during the study (baseline included)
Baseline positive	ADA positive observed at baseline regardless of the post-baseline ADA status
Post-baseline positive	ADA positive observed at least once during post-baseline regardless of the baseline ADA status
Only baseline positive	ADA positive observed at baseline but not observed at any time post-baseline
Only post-baseline positive (treatment-induced)	ADA positive not observed at baseline but observed at least once post-baseline
Both baseline and post-baseline positive	ADA positive observed at baseline and observed at least once post-baseline
Persistent positive	Treatment-induced ADA positive at ≥ 2 post-baseline assessments (with ≥ 16 weeks between first and last positive) or positive at the last post-baseline assessment
Transient positive	Treatment-induced ADA post-baseline positive but does not fulfil the criteria of persistent positive

ADA = anti-drug antibodies.

4.15 Final Analysis

The final analysis will be conducted after all participants have completed the Week 112 Visit or discontinued early from the study.

By study design, the participants may undergo the different [REDACTED] based upon the renal response observed at Week 48 and Week 52. Thus, in the final analysis, the participants will be divided into two subgroups based on their PRR/CRR status at the Week 48 through Week 52:

- PRR/CRR Subgroup: Participants who achieved PRR or CRR at Week 48 and sustained through Week 52 will remain in their treatment groups. Statistical modeling can be used to examine the treatment effect between treatment groups over the Stage II of treatment (i.e., [REDACTED] mg [REDACTED] vs. placebo and [REDACTED] mg [REDACTED] vs. placebo), as applicable. All endpoints defined in primary, secondary and [REDACTED] will be analyzed. Some key endpoints examples are highlighted below.
- Non-PRR/CRR Subgroup: Participants who did not achieve PRR or CRR at either [REDACTED] will be administered daxdilimab [REDACTED] mg SC [REDACTED] through [REDACTED] (last dose administered at [REDACTED]). The final analysis for this subgroup will be descriptive only. No statistical modeling will be performed and no formal statistical comparison between treatment groups will be tested. All endpoints defined in primary, secondary and [REDACTED] except for all time-to-event endpoints, will be analyzed. Some key endpoints examples are highlighted below.

In the final analysis, all analyses planned for the primary analysis will be rerun with the Full Analysis Set.

For the non-PRR/CRR subgroup, the following analyses up to the Week 112 visit will be covered in the final analysis using Stage II Analysis Set:

- Proportion of participants achieving PRR or CRR or [REDACTED] in the Stage II
- Change from baseline in eGFR. In addition, change from re-baseline (Week 64) in eGFR will be explored descriptively
- Change from baseline in UPCR. In addition, change from re-baseline (Week 64) in UPCR will be explored descriptively

- Proportion of participants with prednisone-equivalent dose ≤ 2.5 mg/day for participants with baseline OCS > 2.5 mg/day until Week 92

■ [REDACTED]
■ [REDACTED]
■ [REDACTED]

For the PRR/CRR subgroup, the following analyses using the data up to the Week 112 visit will be covered in the final analysis using Stage II Analysis Set:

- Proportion of participants sustaining PRR or CRR or [REDACTED] in the Stage II
- Time to loss PRR or CRR in the Stage II after achieving PRR/CRR at Week 48 and Week 52
- eGFR slope
- Change from baseline in UPCR
- Proportion of participants with prednisone-equivalent dose ≤ 2.5 mg/day for participants with baseline OCS > 2.5 mg/day until Week 104
- [REDACTED]
■ [REDACTED]

In the final safety analysis, the data up to the Week 112 visit (see Section 4.9) will be used.

Summary statistics will be computed and displayed by treatment group for the PRR/CRR subgroup or by treatment pathway ([REDACTED] mg \rightarrow [REDACTED] mg, [REDACTED] mg \rightarrow [REDACTED] mg, placebo \rightarrow [REDACTED] mg) for the non-PRR/CRR subgroup and by visit, where applicable. Descriptive statistics for continuous variables will minimally include the number of participants, mean of the observed values/change from baseline, SD, minimum, median, and maximum. For categorical variables, frequencies and percentages will be presented. For analyses involved with statistical modeling, the analysis methods are as follows (if applicable):

- Time to loss at least PRR status: Kaplan-Meier cumulative distribution curves will be generated for each treatment group. Participants will be censored at the earliest of their treatment discontinuation time, receipt of rescue therapy, study withdrawal or death or at Week 112 when the event of at least PRR cannot be sustained after Week 52. A corresponding summary table will present the number of participants at risk, the number of participants responding, and the number of participants censored at each postbaseline time point by treatment groups. The table will also present the median, along with the corresponding 2-sided 90% CI of time to response. Cox proportional hazards model will be explored (if applicable) with treatment group included in the model adjusting for eGFR and 24-hour UPCR values collected at Week 52. The hazard ratio with associated 2-sided 90% CIs and p-values will be presented
- For continuous and binary endpoint endpoints, similar analysis methods will be applied as described in Section 4.8.3.2 of the SAP
- [REDACTED]
■ [REDACTED]

A line plot of proportion of PRR, CRR, [REDACTED] over time will also be produced by randomized treatment group or treatment pathway within each of the subgroups. Boxplots of change of [REDACTED] will also be plotted by randomized treatment group or treatment pathway within each of the subgroups.

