4.1.1 Definition of Baseline

Unless otherwise specified, baseline is defined as the last non-missing valid observation prior to the first dose of trial intervention. In cases where baseline measurements are taken on the same day as trial intervention and no times are reported, it will be assumed that these measurements are taken prior to trial intervention being administered.

At [REDACTED] participants from all three Treatment Groups will be assigned to a [REDACTED] [REDACTED] based upon the renal response observed at [REDACTED] [REDACTED]. All participants who did not achieve the primary endpoint will be re-baselined at [REDACTED]. A re-baseline is defined as the last available assessment prior to the first quarterly dose of study intervention administered at [REDACTED].

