4.4.4 Stage II Analysis Set

The stage II analysis set includes all participants who received at least one dose of trial intervention during the Stage II treatment period starting from [REDACTED].

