4.9.2.3 Prior and Concomitant Medications

Prior and concomitant medications and procedures will be summarized using the safety analysis sets accordingly. The details of prior and concomitant medications are described in Section 6.7 of the protocol.

Medications collected at Screening and during the trial will be coded using the current version of the World Health Organization Drug dictionary (WHO-DD). Number (%) of participants who received prior medications and concomitant medications will be summarized by treatment presented by WHO-DD Anatomical Therapeutic Chemical (ATC) category and PT. At each level of summarization, a participant is counted once if the participant reported one or more medications at that level. The summary of prior and concomitant medications during Stage I will be based on safety analysis set. The concomitant medications during Stage II will be summarized based on the second-year analysis set. The prior and concomitant medications are defined as below.

- Prior medications are defined as medications with a stop date occurring before the first trial intervention administration date.

- Concomitant medications during Stage I are defined as follows:
 - Medications with a start date before Week 64 trial intervention administration and stop date on or after the first trial intervention administration date for the participants entering the second-year treatment period.
 - Medications with stop date on or after the first trial intervention administration date for participants not entering the second-year treatment period.
- Concomitant medications for Stage II are defined as medications with a stop date on or after Week 64 daxdilimab administration date.

Rescue therapy for worsening LN may be administered at the discretion of Investigators as clinically indicated. Final rescue therapy will be reviewed and determined before unblinding at the end of Stage I.

Rescue therapy includes:

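### The Stage II sustained-response proportion leaves out Week 52 responders who never receive a Stage II dose, so it is overstated relative to all Week 52 responders

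*SAP*

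**What the plan says.** For the final analysis, SAP 4.15 divides participants by whether they reached PRR or CRR at Week 48 and held it through Week 52. In the responder subgroup, "the following analyses using the data up to the Week 112 visit will be covered in the final analysis using Stage II Analysis Set". The list covers the proportion sustaining response in Stage II and "Time to loss PRR or CRR in the Stage II after achieving PRR/CRR at Week 48 and Week 52". SAP 4.4.4 says that the Stage II Analysis Set "includes all participants who received at least one dose of trial intervention during the Stage II treatment period starting from" a time that is redacted there.

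Other visible text dates that start:

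- SAP 4.1.1: "A re-baseline is defined as the last available assessment prior to the first quarterly dose of study intervention". SAP 4.15 puts a week on it: "change from re-baseline (Week 64) in eGFR will be explored descriptively".
- SAP 4.9.2.3: "Concomitant medications for Stage II are defined as medications with a stop date on or after Week 64 daxdilimab administration date".

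Four further provisions matter:

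- SAP 4.8.1.1 treats rescue or treatment discontinuation as failure in the primary estimand. The PRR definition in SAP 4.8.2.1 carries the same no-discontinuation criterion.
- Under Protocol 7.1.1, someone who stops dosing after Week 52 goes to an end-of-treatment visit and safety follow-up.
- The time-to-loss analysis in SAP 4.15 censors at discontinuation, rescue, withdrawal or death.
- The Full Analysis Set rerun in SAP 4.15 reaches only the outputs already planned for the primary analysis.

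**The concern.** Response is settled at Week 52, but entry to the analysis depends on a dose first due 64 − 52 = 12 weeks later. A responder who stops for good in between is neither a success nor a failure in the sustained proportion.

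Those weeks are not quiet. Steroid tapering is barred from Week 40 to Week 52 and recommended again afterwards (Protocol 6.7.4.1.2). Mycophenolate above 2 gm/day at Week 52 is to come down by Week 60 (Protocol 6.7.4.1.1). Some stops in this window may therefore reflect loss of response, which is what a durability figure should capture.

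The population also does not fit the SAP's own clock. The time-to-loss analysis looks at response after Week 52, and its Cox model adjusts for Week 52 values.

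At stake are the second-year durability proportion and any modelled comparison of each dose with placebo in this subgroup, which SAP 4.15 allows. The Week 52 primary conclusion is not affected.

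**Working it through.** **When Stage II dosing starts.** SAP 4.1.1, 4.9.2.3 and 4.15 together point to Week 64. The Protocol synopsis gives 19 administrations, a quarterly maintenance regimen and a last dose at Week 100. Assuming Day 1, Week 2 and then every 4 weeks from Week 4 to Week 52 (2 + 13 = 15), plus Weeks 64, 76, 88 and 100 (4), the total is 19. This agrees with Week 64. The count alone cannot say to which stage a Week 52 dose belongs; the SAP sections do that.

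**The plan's own figure.** No figure is stated for durability. The sample-size statement (SAP 2.3: 25% versus 45%, 70 per arm, two-sided alpha 0.10) reproduces: power is 80.4% against a stated 80%. Its rates serve below only to show the likely size of the subgroup.

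**Size of the overstatement.** Let q be the share of Week 52 responders with no Stage II dose, and s the share sustaining among those dosed. The SAP reports s. With leavers counted as failures, the proportion in all responders is s(1 − q), so the overstatement is s × q. The documents give neither s nor q; both are assumed.

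| q (s = 80%) | SAP proportion | All responders | Overstatement |
|---|---|---|---|
| 0% | 80.0% | 80.0% | 0 |
| 2% | 80.0% | 78.4% | 1.6 points |
| 5% | 80.0% | 76.0% | 4.0 points |
| 10% | 80.0% | 72.0% | 8.0 points |
| 15% | 80.0% | 68.0% | 12.0 points |

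For s from 60% to 90% and q from 2% to 15%, the range is 0.60 × 2% = 1.2 points to 0.90 × 15% = 13.5 points.

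**In whole participants.** The planning CRR rates are a floor for the PRR/CRR subgroup: 70 × 0.45 ≈ 32 responders on a daxdilimab dose and 70 × 0.25 ≈ 18 on placebo. Suppose two leave in each arm.

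- Daxdilimab, 24 sustaining: 24/30 = 80.0% under the SAP, 24/32 = 75.0% in all responders.
- Placebo, 13 sustaining: 13/16 = 81.3% under the SAP, 13/18 = 72.2% in all responders.

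**Treatment difference.** Take s = 80% on daxdilimab and 70% on placebo, a 10-point difference under the SAP. In all responders:

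- 5% leaving in both arms: 76.0 − 66.5 = 9.5 points.
- 15% on daxdilimab, 5% on placebo: 68.0 − 66.5 = 1.5 points.
- 5% on daxdilimab, 15% on placebo: 76.0 − 59.5 = 16.5 points.

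**Time to loss.** Take 30 dosed responders with losses at Week 64 (2), Week 76 (2), Week 88 (1) and Week 100 (1). The Kaplan-Meier estimate at Week 104 is (28/30)(26/28)(25/26)(24/25) = 0.80. Add two leavers censored at Week 58, as SAP 4.15 would have it. The next scheduled 24-hour UPCR after Week 52 is at Week 64 (Protocol 8.1), where the number at risk is still 30, so the estimate stays at 0.80. Counted as events at Week 58, they give (30/32) × 0.80 = 0.75. Only an unscheduled sample showing loss before the stop would let the change of set alone matter.

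**The case against.** The best defence is that the endpoints are worded as response in Stage II. Durability among people who start the maintenance regimen is a coherent question. Not every leaver has lost renal response: pregnancy, withdrawal of consent or an unrelated adverse event can also end dosing (Protocol 7.1.1). The word overstated is therefore relative to a chosen target. This stands as a limit. However, the SAP's own response definitions require no discontinuation, so counting leavers as not sustained applies its existing rule.

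The disposition table (SAP 4.5) shows Stage I completion, discontinuation with reasons, and entry to Stage II. That gives some view of attrition, but not by responder status.

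A reader might also infer more than the documents support:

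- *That the choice of set inflates the Kaplan-Meier curve.* It does not; the censoring rule does, as the example shows.
- *That Weeks 52 to 64 are immortal time, so anyone who flares then disappears.* A flare alone excludes nobody. Study intervention may continue after rescue with Medical Monitor approval (Protocol 6.7.6), and such a person stays in the set if dosed in Stage II.
- *That a Week 64 dose is required.* Any Stage II dose suffices, so missing Week 64 and being dosed later keeps the participant in.
- *That no other durability analysis exists.* SAP 4.15 presents its lists as examples, and much exploratory text is redacted. None is visible, which is all that can be said.

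**Conclusion.** The point holds for the proportion sustaining response. Week 52 responders who permanently stop or leave before any Stage II dose are outside its denominator, and no visible analysis restores them. Relative to all Week 52 responders with leavers counted as failures, the overstatement is s × q: 1.6 to 12 points for an assumed s of 80% and q of 2% to 15%, and zero if nobody leaves. These sizes are hypothetical. The direction of the effect on the treatment difference is not fixed. The Week 64 start is inferred, though from several agreeing sections. For time to loss, the set and the censoring rule have to be dealt with together. The change should be made, but it concerns the final analysis and not the primary test.

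**What to change.** In SAP 4.15, compute the sustained-response proportion in all Full Analysis Set participants with PRR or CRR at Week 48 sustained through Week 52, and count those with no Stage II dose as not sustained.

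For time to loss, use the same population with time zero at the Week 52 assessment. Revise the censoring rule so that treatment discontinuation and rescue count as loss of response and, for consistency with the proportion, withdrawal and death as well. Keep the Stage II Analysis Set version as a supplementary analysis.

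The cost is SAP wording; the data are already collected. Reported durability becomes slightly less favourable if anyone leaves, and some leavers counted as failures may not truly have lost renal response. The supplementary version shows how much depends on that choice.

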3. OBJECTIVES AND ENDPOINTS

Primary Objective	Primary Endpoint
To evaluate the efficacy of daxdilimab in combination with SOC compared to placebo in combination with SOC in participants with active, proliferative LN.	Proportion of participants achieving Complete Renal Response (CRR) at [REDACTED] CRR is defined as meeting all of the following: 
• Estimated glomerular filtration rate (eGFR) \geq 60 mL/min/1.73m² or no worse than 15% below baseline• 24-hour UPCR \leq 0.5 mg/mg• No discontinuation of study intervention or use of restricted medication beyond the protocol allowed threshold before assessment
Secondary Objectives	Secondary Endpoints
To assess overall renal response (ORR) (defined as CRR plus partial renal response [PRR]) with daxdilimab versus placebo in participants with active, proliferative LN.	Proportion of participants achieving ORR at [REDACTED] See above for definition of CRR. PRR is defined as meeting all of the following: 
• eGFR \geq 60 mL/min/1.73m² or no worse than 15% below baseline• Improvement in 24-hour UPCR:
– For participants with a baseline UPCR \leq 3.0 mg/mg: < 1.0 mg/mg– For participants with a baseline UPCR $>$ 3.0 mg/mg: $> 50\%$ improvement from baseline and ≤ 3.0 mg/mg• No discontinuation of study intervention or use of restricted medication beyond the protocol allowed threshold before assessment
To assess the change from baseline in eGFR with daxdilimab versus placebo in participants with active, proliferative LN.	
• Change from baseline in eGFR at Week 52.

To evaluate the ability to improve dose requirements of oral corticosteroids (OCS) with daxdilimab versus placebo in participants with active, proliferative LN.	
Proportion of participants able to taper OCS to ≤ 2.5 mg/day prednisone-equivalent by Week 24 and maintain this dose through Week 52.
 
Sustained reduction of OCS dose:
 
• Prednisone-equivalent dose ≤ 2.5 mg/day by Week 24 and not exceeding this dose through Week 52 and• No discontinuation of study intervention or use of restricted medication beyond the protocol allowed threshold before assessment

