7.1.1. Discontinuation of Study Intervention

Blinded study intervention will be discontinued in participants who meet pre-defined criteria for worsening LN or SLE.

Criteria for discontinuing study intervention for worsening LN or SLE (at any time):

- > 30% decrease in eGFR compared to baseline due to LN **and** eGFR < 60 mL/min/1.73 m² (compared to the average of the previous two visits, not explained by change in comorbidities or concomitant medications. A decrease in eGFR must be confirmed on at least two independent samples at least 5 days apart after non-SLE causes have been corrected or excluded) **OR**
- Increase in renal or extra-renal lupus activity requiring prohibited systemic immunosuppressive treatment (eg, cyclophosphamide, rituximab, belimumab) **OR**
- Receipt > 1 methylprednisolone pulse after the day of Randomization **OR**
- Receipt of any methylprednisolone pulse after Week 8 **OR**
- The study intervention will be discontinued if MMF is discontinued, and another immunosuppressant is initiated

Criteria for discontinuing study intervention for worsening LN or SLE at Week 12 and Week 24:

- eGFR < 75% of baseline and < 60 mL/min/1.73 m² (compared to the average of the previous two visits, not explained by change in comorbidities or concomitant medications. A decrease in eGFR must be confirmed on at least two independent samples at least 5 days apart after non-SLE causes have been corrected or excluded) **OR**
- Nephrotic range UPCR (confirmed by a second measurement at least two weeks after the first measurement):
 - Participants with 24-hour UPCR \leq 3 mg/mg at baseline will be withdrawn if 24-hour UPCR increases by > 50% from baseline to > 3.5 mg/mg
 - Participants with 24-hour UPCR > 3 mg/mg at baseline will be withdrawn if 24-hour UPCR **at Week 24** > 3.5 mg/mg and there is < 50% improvement from baseline

OR

- Inability to adhere to corticosteroids requirements:
 - Inability to reduce OCS to \leq 15 mg/day prednisone-equivalent at Week 12
 - Inability to reduce OCS to \leq 10 mg/day prednisone-equivalent by Week 24

Participants who exceed the maximum daily OCS dose at the Week 12 or Week 24 Visits may continue to receive study intervention if the current dose is part of a temporary increase in OCS dose (eg, protocol allowed burst and taper). Participants who cannot be returned to their pre-increase dose within 14 days from the start of the increase will have their study intervention discontinued at the next visit.

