4.8.2 Secondary Efficacy Endpoints and Analyses

4.8.2.1 Secondary Efficacy Endpoints and Estimands

The estimand for the binary secondary efficacy endpoints is defined as follows, using composite variable strategy to address intercurrent events.

1. Population:

- a. ORR: Participants in the Full Analysis Set.
- b. Sustained reduction of oral corticosteroids (OCS) dose: Participants in the Full Analysis Set whose Baseline OCS dose is greater than 2.5 mg/day prednisone equivalent (Appendix 1).

2. Variables (outcome measures):
 - a. ORR at Week 48 and sustained through Week 52 (ORR is defined as CRR or PRR). CRR was defined in primary endpoint. PRR is defined by meeting the following criteria:
 - i. $eGFR \geq 60 \text{ mL/min}/1.73\text{m}^2$ or no worse than 15% below baseline.
 - ii. Improvement in 24-hour UPCR:
 - For participants with a baseline UPCR $\leq 3.0 \text{ mg/mg}$: $< 1.0 \text{ mg/mg}$
 - For participants with a baseline UPCR $> 3.0 \text{ mg/mg}$: $> 50\%$ improvement from baseline and $\leq 3.0 \text{ mg/mg}$
 - iii. No use of restricted medication beyond the protocol allowed threshold before assessment.
 - iv. No discontinuation of study intervention.
- b. Response in sustained reduction of OCS dose, which is defined by meeting the following criteria:
 - i. Prednisone-equivalent dose $\leq 2.5 \text{ mg/day}$ by Week 24 and not exceeding this dose through Week 52.
 - ii. No use of restricted medication beyond the protocol allowed threshold before assessment.
 - iii. No discontinuation of study intervention.

3. Intercurrent event:
 - a. Rescue medications: Captured in the variable definition.
 - b. Treatment discontinuation: Captured in the variable definition.
4. Population-level summary: Difference in proportions of responders between the daxdilimab group and placebo group.

The estimand of change from baseline in eGFR at Week 52 is defined as follows, using hypothetical strategy to address intercurrent event of rescue medications by assuming data is missing as missing at random (MAR) after rescue medication and treatment policy strategy to address intercurrent event of treatment discontinuation by continue taking measures regardless of treatment discontinuation.

1. Population: Participants in the Full Analysis Set.

2. Variable (outcome measure): Change from baseline in eGFR at Week 52.
The baseline values of eGFR are defined in Section 4.8.1.2
3. Intercurrent event:

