The initiation of any new treatment for lupus or LN with the selected restricted medications or prohibited medications as a rescue. Participants who receive rescue therapy will be considered treatment failures for subsequent endpoint analyses (such as CRR). Detailed prohibited medications are defined in the protocol Section 6.7.2, restricted medications are defined in the protocol Section 6.7.3, and rescue medicine is defined in the protocol Section 6.7.6. Additionally, certain other concomitant medications initiated after randomization beyond those allowed in protocol Section 6.7.5 may also constitute rescue therapy.

The number and percentage of participants who received rescue therapy will be summarized by treatment group according to the defined criteria using the Safety Analysis Set for Stage I and using Stage II Analysis Set for Stage II by WHO-DD ATC category and PT set.

- New Treatment

The number and percentage of participants who received the new treatment will be summarized.

- MMF/MPA

The number and percentage of participants who received MMF/MPA at above allowed dose by the time window will be summarized.

- Corticosteroids

The number and percentage of participants who received corticosteroids beyond the one allowed steroid bursts, increases in corticosteroids for the prevention of adrenal insufficiency, or during the required stable dose time window from baseline will be summarized.

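### Time to loss of PRR censors at treatment discontinuation and rescue, which the SAP's own rules count as non-response, and the same sentence puts the loss event inside the censoring clause

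*SAP*

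**What the plan says.** SAP 4.15 (Final Analysis) follows participants who reached PRR or CRR at Week 48 and held it through Week 52, and plans a time-to-loss analysis over Stage II.

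- **Censoring rule:** "Participants will be censored at the earliest of their treatment discontinuation time, receipt of rescue therapy, study withdrawal or death", continuing "or at Week 112 when the event of at least PRR cannot be sustained after Week 52".
- **Table for this endpoint:** it counts participants at risk, responding and censored. "The table will also present the median, along with the corresponding 2-sided 90% CI of time to response".
- **Model:** a Cox model will be explored if applicable, adjusted for Week 52 eGFR and 24-hour UPCR, with hazard ratios, 90% CIs and p-values.
- **Companion summary in the same subgroup:** "Proportion of participants sustaining PRR or CRR or" a further, redacted item.

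Elsewhere the plan defines response as follows.

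- **Protocol Section 3, repeated in SAP Table 1:** PRR requires "No discontinuation of study intervention or use of restricted medication beyond the protocol allowed threshold before assessment".
- **SAP 4.8.2.1:** this is restated as separate PRR items, the last being "No discontinuation of study intervention", under a composite strategy for the binary secondary endpoints.
- **SAP 4.9.2.3:** "Participants who receive rescue therapy will be considered treatment failures for subsequent endpoint analyses (such as CRR)".

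**The concern.** The endpoint is loss of PRR. Discontinuation ends PRR by definition, and rescue makes the participant a failure by a general rule. The time-to-event analysis nevertheless treats both as censored, which says that loss was not observed. The Kaplan-Meier display could then disagree with the sustained-response proportion planned for the same people, if that proportion uses the standard definition.

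Some of this censoring is also plausibly related to disease course. Protocol 7.1.1 stops study intervention at any time for "Increase in renal or extra-renal lupus activity requiring prohibited systemic immunosuppressive treatment", for a methylprednisolone pulse after Week 8, or when MMF is replaced by another immunosuppressant. Scheduled 24-hour UPCR in this period falls only at Weeks 64, 76, 88, 100 and 104 (Protocol 8.1), so rescue between visits can come before any recorded laboratory loss. Participants who stop dosing after Week 52 go only to the End-of-Treatment Visit and Safety Follow-Up.

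The wording is a second problem. Read literally, failing to sustain PRR is a reason for censoring at Week 112. The response labels in the table do not fit a loss endpoint.

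**Working it through.** **Reproducing the plan's figure.** There is none to reproduce: no rate, power or sample size is stated for this endpoint.

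**The rules side by side**

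| Occurrence after Week 52, no earlier laboratory loss | PRR definition and failure rule | SAP 4.15 curve |
|---|---|---|
| Study intervention discontinued | PRR not met | Censored |
| Rescue therapy | Treatment failure | Censored |
| PRR not sustained | Loss | Event by the endpoint's name, censored by the literal sentence |

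**Direction.** Censoring a participant and counting an event remove that person from the risk set at the same time. Counting the event also multiplies the Kaplan-Meier product by a factor below 1. The SAP curve is therefore above retention under the SAP's PRR definition from the first such event onward.

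**Where censoring is less of a worry.** The eGFR stopping rule in Protocol 7.1.1 usually fails PRR first. At baseline eGFR 80, dosing stops below 0.70 × 80 = 56. The PRR eGFR item fails below both 60 and 0.85 × 80 = 68, that is, below 60. Such cases may already be recorded as laboratory losses.

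**Size (all rates assumed).** Take laboratory loss at probability l per 12 weeks from Week 52, and rescue or discontinuation at r per 12 weeks from Week 64, independent of each other. Let h(p) = −ln(1 − p).

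- SAP curve at Week 104: exp[−h(l) × 52/12]
- PRR definition at Week 104: exp[−h(l) × 52/12 − h(r) × 40/12]

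For l = 5%, h(l) × 52/12 = 0.0513 × 4.333 = 0.222, so the SAP curve shows exp(−0.222) = 0.801. Adding h(0.04) × 40/12 = 0.0408 × 3.333 = 0.136 gives exp(−0.358) = 0.699.

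| l | SAP curve | r = 2% | r = 4% | r = 6% |
|---|---|---|---|---|
| 5% | 0.801 | 0.749 | 0.699 | 0.651 |
| 8% | 0.697 | 0.651 | 0.608 | 0.567 |

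A simulation of 400,000 participants with l = 5%, recording laboratory loss only at the scheduled visits, gave the same retention to within 0.001. It censored 5.9%, 11.4% and 16.8% at rescue or discontinuation before any recorded laboratory loss.

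**Hazard ratio to Week 104, daxdilimab to placebo.** With at-risk fraction Y = exp[−h(l)t/12 − h(r)·max(t − 12, 0)/12], t in weeks from Week 52, and total hazards h_d and h_p, the Cox log hazard ratio b solves

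∫ { h_d·Y_d − [Y_d·e^b / (Y_d·e^b + Y_p)]·(h_d·Y_d + h_p·Y_p) } dt = 0.

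| l (daxdilimab, placebo) | r (daxdilimab, placebo) | SAP rule | PRR definition |
|---|---|---|---|
| 5%, 5% | 2%, 6% | 1.00 | 0.683 |
| 5%, 5% | 6%, 2% | 1.00 | 1.464 |
| 3%, 6% | 4%, 4% | 0.492 | 0.659 |

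Simulations with 400,000 per arm gave 0.677, 1.463 and 0.657 in continuous time, and 0.671, 1.477 and 0.666 with laboratory loss recorded at visits.

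**Informative censoring alone.** The figures above come from the change of event definition. A separate simulation used a shared gamma frailty (variance 1) to link the two processes from Week 52 to Week 112, with 20% net laboratory loss. The censored Kaplan-Meier estimate of loss was 19.2%, 18.3% and 17.4% for intercurrent risks of 10%, 20% and 30%.

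**The case against.** The strongest defence is that censoring may be a deliberate while-on-treatment or hypothetical target. The composite strategy is written out for CRR, ORR and OCS reduction, not for this endpoint, and the SAP does vary strategy by endpoint. The failure rule in 4.9.2.3 is general and covers rescue only. Much of SAP 4.8.3 and parts of 4.15 are redacted and could hold an event definition. Under independent risks the censored curve is unbiased for laboratory loss, so the 5 to 15 point gap reflects the choice of event. Dependence alone moves the estimate by only 0.8 to 2.6 points in the frailty illustration.

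The subgroup will also be small. If 18 to 45 of 70 per arm respond (an assumption), 6% to 17% censored is about 1 to 8 people per arm. In the 2% against 6% case, expected losses under the PRR definition are 0.251n and 0.349n. The standard error of the log hazard ratio is then √(1/0.251n + 1/0.349n), from 0.62 down to 0.39, so the shift of ln 0.683 = −0.38 is within one standard error.

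Much of this limits the size of the point, and the redaction limits confidence. It does not remove the conflict. Where the SAP uses a hypothetical strategy, for eGFR in 4.8.2.1, it names it and gives the missing-at-random assumption. Nothing of the kind is visible here, and the gap is measured against the SAP's own PRR definition. The misplaced clause and the wrong labels are in visible text. It is fair that the endpoint's name makes the literal miscoding unlikely; the probable intent was to censor at Week 112 those still in response.

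**Conclusion.** The concern holds, with medium confidence because redacted text might reconcile the rules. As written, the time-to-loss analysis contradicts the SAP's PRR definition and its treatment-failure rule, and its censoring sentence cannot be programmed literally.

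The direction of the curve's error against that definition is certain wherever a rescue or discontinuation comes before laboratory loss. The amount is not known: 5 to 15 points at Week 104 under the 5% assumption, 5 to 13 under the 8% assumption. The hazard ratio can move either way.

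The consequence is confined to this display and its hazard ratio. It is a final-analysis endpoint in the responder subgroup, outside the Type I error procedure, and the Week 52 results are unaffected. The number censored, the sustained-response proportion and the Stage II discontinuation and rescue tables would let a careful reader see the gap. It should be corrected before the final analysis.

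**What to change.** Rewrite the rule in SAP 4.15:

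- **Event:** the first failure of any PRR criterion after Week 52, including discontinuation of study intervention, rescue therapy, or restricted medication beyond the threshold, dated when it occurs.
- **Censoring:** only participants still in response, at study withdrawal without such an event or at the last scheduled renal assessment. State how death is handled.
- **Wording:** remove the clause about response not being sustained from the censoring rule, and relabel the table as time to loss.
- **Sensitivity analysis:** keep the present censoring, with its hypothetical estimand stated.
- **Consistency:** state that the sustained-response proportion uses the same definition.

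The cost is one sentence, one table label and one event flag, all from dates already collected. Retention will look less favourable. Reasons unrelated to efficacy, such as pregnancy or an extra steroid burst for a non-SLE cause, will count as loss, as the existing response rules already imply.
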